1282 The circumstances of all reportable cases of the following will be summarized and tabulated by
1283 treatment group:

1284 • Severe hypoglycemia (as defined in Section 8.1)
1285 • Diabetic ketoacidosis (as defined in Section 8.1)
1286 • Other serious adverse events (SAE) and serious adverse device events (SADE)
1287 • Unanticipated adverse device effects (UADE)

1288
1289 The total number of SH or DKA events per subject will be compared using robust Poisson regression
1290 and the percentage of subjects with at least one event will be compared using Fisher's exact test.

1291
1292 **10.6 Additional Tabulations**
1293 The following tabulations will be performed without statistical testing:

1294 - baseline demographics and clinical characteristics
1295 - flow chart accounting for all subjects for all visits
1296 - visit completion rates for each follow-up visit
1297 - hours of sensor use
1298 - days of sensor use per week
1299 - phone contact completion rates for each follow-up visit
1300 - protocol deviations
1301 - number and reasons for unscheduled visits and phone calls
1302 - device malfunctions requiring study team contact and other reported device issues
1303 - In addition, performance metrics will be tabulated, describing the inControl Advice system and
1304 its components.

1305
1306 **10.7 Interim Analysis**
1307 All CGM-related study endpoints will be analyzed for the first 6 weeks of study intervention in the
1308 first 40 subjects. The purpose of the interim analysis is to support regulatory submissions for the
1309 CGM+DSS system.

1310

1311 **11 DATA COLLECTION AND MONITORING**

1312 **11.1 Case Report Forms and Device Data**

1313 The main study data are collected through a combination of case report forms (CRFs) and electronic
1314 device data files obtained from the study software and individual hardware components. These
1315 electronic device files and electronic CRFs from the study website are considered the primary source
1316 documentation.

1317 **11.2 Document Storage and Retention**

1318 The Investigator of each clinical site will retain all records and documents pertaining to this study.
1319 They will be available for inspection by the appropriate regulatory agencies. In addition, the
1320 Investigator will retain the source documents from which the information entered on the CRFs was
1321 derived. These records are to be retained in a secure storage facility maintained by the investigational

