204 on a standard Android smartphone and uses Bluetooth (BT) to communicate with a CGM and Near
205 Field Communication (NFC) to communicate with insulin pens. Currently, inControl runs on a
206 modified release of the Android operating system (OS). Modifications of the OS include the removal
207 of unnecessary applications and functions, and fixes to the BT stack to permit communication with
208 peripheral medical devices. The local inControl module is an Android application with a JS/CSS UI.
209

•

210 inControl-AP: When running closed-loop control, inControl-AP communicates with an insulin pump
211 and modulates insulin delivery automatically to keep blood glucose in a target range. inControl-AP
212 operates on a 5-minute cycle based on the highest frequency of input data. There are three insulin
213 dosing modes (stopped, pump and closed loop) and three operating modes (normal, sleep and

214 exercise). The combination of insulin dosing mode and operating mode determines what actions
215 inControl-AP will perform and what options are presented to the user.

216 inControl-Cloud is an external server system that communicates with the Network Service within
217 inControl-AP over a secure SSL to:

218 • Allow the patient to log in with their inControl-Cloud ID;
219 • Deliver user biometric data (height, weight, date of birth etc.) and therapy profile information
220 (basal rate, carbohydrate to insulin ratio, correction factor).

221 inControl Advice: In this protocol, we now intend to use inControl-Advice, which is designed to
222 provide advice to users, instead of directly controlling the insulin delivery system. inControl Advice
223 shares many of the features of inControl-AP described above, but does not implement automated
224 insulin delivery and receives data from an insulin pen. Instead of automated 5-min adjustments to the
225 insulin delivery, the system provides a series of real-time alerts and on-demand advice, for both dosing
226 of insulin and ingestion of carbohydrates, based on data collected from T1DM patients (i.e.
227 carbohydrate consumption, insulin injected, CGM) and inControl Cloud analytics. inControl Advice
228 includes 6 modules:

229 1. Retrospective analysis of the past few weeks, based on replay simulation technologies which
230 optimizes the patient's functional insulin therapy parameters (basal doses, insulin sensitivity
231 (ISF) factors, and carbohydrate ratios);

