759 Subjects in both groups will be provided with the software needed to download the study CGM
760 and transmit the data to study personnel and will be asked to do so prior to scheduled phone
761 contacts for the remainder of the study.

762 **5.2 Procedures for the CGM+DSS Group**

763 **5.2.1 DSS Training**

764 Subjects randomized to the CGM+DSS group will receive DSS training.

765 The subject will be trained by qualified study staff to use the DSS (inControl Advice) APP to
766 calculate insulin doses for meals and corrections. Prior to initial use, the inControl system will be
767 initialized by a study team member with each subject's individual insulin dosing parameters,
768 including carbohydrate ratio, insulin sensitivity factor and basal insulin dose.

769 Study team members will train the subject in performing specific tasks including the following:

- 770 • The study team will confirm the carbohydrate counting parameters entered in the system
771 with the study physician.
- 772 • How to activate the "meal" screen of the inControl system any time insulin will be given
773 with a meal and the "add correction" screen any time additional correction insulin is
774 desired
- 775 • How to use the NFC communication on the insulin pens to inform and confirm on the
776 inControl system that an insulin dose was injected.
- 777 • How to inform the system of hypoglycemia treatment via a "hypoglycemia treatment"
778 button on the inControl user interface after glucose is consumed that is not accompanied
779 by an insulin bolus
- 780 • What to do when exercising while using the system and how to react to the exercise
781 advice given
- 782 • How to react to the hypoglycemia risk alarm.
- 783 • How to access the bedtime button and react to the possible advice for a bedtime snack.

784 The subject will also be instructed to contact study staff during periods of illness with an
785 elevated temperature >101.5 degrees Fahrenheit (38.6 degrees Celsius), periods of significant
786 illness, or during periods of use of medications such as epinephrine (e.g. for the emergency
787 treatment of a severe allergic reaction or asthma attack) or oral or injectable glucocorticoids to
788 determine if study procedures should be temporarily discontinued.

789 Subjects will be given the inControl Advice device and will be provided with sufficient supplies
790 to last until the final clinic visit.

791 **5.3 Procedures for the CGM Group**

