930 **7.1.2 Safety Measures**

931

932 **7.1.2.1 Hypoglycemia Safety Protocol**

933 All subjects will be required to set the CGM hypoglycemia threshold alarm to a value no less than 70
934 mg/dL.

935

936 If a subject receives a CGM hypoglycemia threshold alarm or notes that the CGM glucose is <70
937 mg/dL, confirmatory fingerstick testing will be recommended and the subject will be instructed to treat
938 hypoglycemia with ~16 grams of fast-acting oral glucose.

939

940 **7.1.2.2 Hyperglycemia Safety Protocol**

941 Subjects will be required to set the CGM hyperglycemia threshold alarm to a value no greater than 300
942 mg/dL.

943

944 If a subject receives a CGM hyperglycemia threshold alarm or notes that the CGM glucose is ≥ 300
945 mg/dL, confirmatory fingerstick testing will be recommended.

946

947 If a subject's CGM reading is ≥ 300 mg/dL for over 1 hour, or ≥ 400 mg/dL at any point, the subject
948 will be instructed to take the following steps:

949

950 • Perform a blood ketone measurement with the study ketone meter. Subjects will also be
951 encouraged to check ketones if they are clinically concerned.

952 • Correction insulin may be taken per the subject's usual routine (CGM group) or per the
953 inControl Advice recommendation (CGM+DSS group).

954 • Subjects will be instructed to administer correction insulin per the subject's usual routine
955 (CGM group) or per the inControl Advice recommendation (CGM+DSS group) for ketones
956 ≥ 0.6 mmol/L and to additionally notify study staff for ketones ≥ 3.0 mmol/L.

957

958 **7.1.2.3 Study System Failure**

959 If the inControl Advice APP stops working, subjects will be instructed to resume their regular home
960 insulin therapy until he/she can contact study staff for confirmation of the current carbohydrate
counting parameters or until the study system can be repaired or replaced.

961 **8 ADVERSE EVENTS, DEVICE ISSUES, POTENTIAL RISKS, AND STOPPING RULES**

962 **8.1 Adverse Event Definition**

963 A reportable adverse event for this protocol includes any untoward medical occurrence that meets
964 criteria for a serious adverse event or any unanticipated medical occurrence in a study subject that is
965 study- or device-related, including severe hypoglycemia as defined below and severe
966 hyperglycemia/diabetic ketoacidosis (DKA) as defined below. Skin reactions from sensor placement
967 are only reportable if severe and/or required treatment.

968

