969 Hypoglycemic events are recorded as Adverse Events (severe hypoglycemic event) if the event
970 required assistance of another person due to altered consciousness, and required another person to
971 actively administer carbohydrate, glucagon, or other resuscitative actions. This means that the
972 participant was impaired cognitively to the point that he/she was unable to treat himself/herself, was
973 unable to verbalize his/ her needs, was incoherent, disoriented, and/or combative, or experienced
974 seizure or coma. These episodes may be associated with sufficient neuroglycopenia to induce seizure
975 or coma. If plasma glucose measurements are not available during such an event, neurological
976 recovery attributable to the restoration of plasma glucose to normal is considered sufficient evidence
977 that the event was induced by a low plasma glucose concentration.

978
979 Hyperglycemic events are recorded as Adverse Events (severe hyperglycemic event) if the event
980 involved DKA, as defined by the Diabetes Control and Complications Trial (DCCT) and described
981 below, or in the absence of DKA if evaluation or treatment was obtained at a health care provider
982 facility for an acute event involving hyperglycemia with ketosis.

983
984 Hyperglycemic events are classified as DKA if the following are present:

- 985 • Symptoms such as polyuria, polydipsia, nausea, or vomiting;
- 986 • Serum ketones >1.5 mmol/L or large/moderate urine ketones;
- 987 • Either arterial blood pH <7.30 or venous pH <7.24 or serum bicarbonate <15 ; and
- 988 • Treatment provided in a health care facility

989 **8.2 Recording of Adverse Events**

990 Throughout the course of the study, all efforts will be made to remain alert to possible adverse events
991 or untoward findings. The first concern will be the safety of the study participant, and appropriate
992 medical intervention will be made.

993
994 All reportable adverse events whether volunteered by the subject, discovered by study personnel
995 during questioning, or detected through physical examination, laboratory test, or other means will be
996 reported on an adverse event form online. Each adverse event form is reviewed by the Medical
997 Monitor at the Coordinating Center to verify the coding and the reporting that is required.

998
999 The study investigator will assess the relationship of any adverse event to be related or unrelated by

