1102 As with any person having type 1 diabetes and using insulin, there is always a risk of having a low
1103 blood sugar (hypoglycemia). The frequency of hypoglycemia should be no more and possibly less
1104 than it would be as part of daily living. Symptoms of hypoglycemia can include sweating, jitteriness,
1105 and not feeling well. Just as at home, there is the possibility of fainting or seizures (convulsions) and
1106 that for a few days the subject may not be as aware of symptoms of hypoglycemia. A CGM
1107 functioning poorly and significantly over-reading glucose values could lead to inappropriate insulin
1108 delivery. Inadvertent mix-ups of short-acting and long-acting insulins could contribute to the risk of
1109 hypoglycemia.

1110

1111 **8.5.5 Risk of Hyperglycemia**

1112 Hyperglycemia and ketonemia could occur if insulin delivery is attenuated or suspended for an
1113 extended period. A CGM functioning poorly and significantly under-reading glucose values could
1114 lead to an inappropriate insulin recommendation. Inadvertent mix-ups of short-acting and long-acting
1115 insulins could contribute to the risk of hyperglycemia.

1116

1117 **8.5.6 Risk of Device Reuse**

1118 The study CGM system is labeled for single-patient use only. The sensor (the component of the system
1119 that enters the skin) will be single-patient use only. The transmitter and receiver may be reused during
1120 the study after cleaning the device using a hospital-approved cleaning procedure. The transmitter is

1121 attached to the sensor but does not enter the skin and the receiver is a hand held device. Subjects will
1122 be informed that FDA or relevant national authorities have approved these devices for single use and
1123 that by using them among multiple patients, bloodborne pathogens (i.e. Hepatitis B) may be spread by
1124 multiple users.

1125

1126 **8.5.7 Psychosocial Questionnaires**

1127 As part of the study, participants will complete psychosocial questionnaires which include questions
1128 about their private attitudes, feelings and behavior related to diabetes. It is possible that some people
1129 may find these questionnaires to be mildly upsetting. Similar questionnaires have been used in
1130 previous research and these types of reactions have been uncommon.

1131

1132 **8.5.8 Other Risks**

1133 Some subjects may develop skin irritation or allergic reactions to the adhesives used to secure the

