1134 CGM. If these reactions occur, different adhesives or “under-taping” (such as with IV 3000,
1135 Tegaderm, etc.) will be tried, sites will be rotated frequently, and a mild topical steroid cream or other
1136 medication may be required.

1137 Whenever the skin is broken there is the possibility of an infection. The CGM sensors are inserted
1138 under the skin. It is possible that any part that is inserted under the skin may cause an infection. These
1139 occur very infrequently, but, if an infection was to occur, oral and/or topical antibiotics can be used.
1140 The risk of skin problems could be greater if you use a sensor for longer than it is supposed to be used.
1141 Therefore, participants will be carefully instructed about proper use of the sensor.

1142 Data downloaded from the CGM and blood glucose and ketone meters will be collected for the study
1143 as measures of diabetes self-management behaviors. Some people may be uncomfortable with the
1144 researchers' having such detailed information about their daily diabetes habits.

1145

1146 **8.6 Study Stopping Criteria**

1147

1148 **8.6.1 Subject Discontinuation of Study Treatment**

1149 Rules for discontinuing inControl Advice (if randomized to CGM+DSS group) or study CGM use (if
1150 randomized to the CGM group) are as follows:

- 1151 1. One episode of severe hypoglycemia, or of hyperglycemia/DKA as defined in Section 8.1
- 1152 2. One serious adverse event related to device malfunction.
- 1153 3. The subject requests that the treatment be stopped
- 1154 4. Subject pregnancy

1155

1156 **8.6.2 Criteria for Suspending/Stopping Overall Study**

1157 In the case of inControl Advice resulting in a severe hypoglycemia or severe hyperglycemia event (as
1158 defined in Section 8.1) that is thought to be advice-related (due to excess insulin administration) and
1159 occurs more than three times, the overall study will be suspended while the problem is diagnosed. The
1160 study may resume if the underlying problem can be corrected by a protocol or system modification that
1161 will not invalidate the results obtained prior to suspension. The overall study will be stopped in the
1162 event of three serious adverse events related to device malfunction.

1165 **9 MISCELLANEOUS CONSIDERATIONS**

1166 **9.1 Benefits**

1168 One purpose of this research is to reduce the frequency of hypoglycemia and severe hypoglycemic

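### The suspension rule in Section 8.6.2 names severe hyperglycemia but ties advice-related events to excess insulin, so read literally DKA from advice that was too low never counts

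*Combined protocol and SAP*

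**What the plan says.** Section 8.6.2 opens the suspension rule with "In the case of inControl Advice resulting in a severe hypoglycemia or severe hyperglycemia event (as" and continues "defined in Section 8.1) that is thought to be advice-related (due to excess insulin administration) and". The event must occur more than three times, so the fourth qualifying event triggers suspension. A separate sentence stops the study at three serious adverse events related to device malfunction.

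Section 8.1 gives the definition that the rule relies on. It begins "Hyperglycemic events are recorded as Adverse Events (severe hyperglycemic event) if the event" and then lists two routes: DKA by the DCCT definition, or, without DKA, evaluation or treatment at a health care facility for acute hyperglycemia with ketosis.

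Section 8.5.5 gives the protocol's own account of how hyperglycemia could arise. It names reduced or interrupted insulin delivery, and then says: "A CGM functioning poorly and significantly under-reading glucose values could" "lead to an inappropriate insulin recommendation".

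**The concern.** The rule names two events that lie in opposite directions of dosing error, but its only causal wording covers one direction. If the parenthesis governs both events, a run of DKA cases caused by doses that were too small would not suspend the study, although severe hyperglycemia is one of the two events the rule was written for. DKA is a main safety endpoint (Section 1.3.7), and the protocol classes this as a significant risk device study because inControl Advice is experimental (Section 1.4). If instead the parenthesis is read as belonging to hypoglycemia only, the rule works, but nothing tells the reader to take it that way. Two people applying the same text could reach different counts toward a study-wide threshold.

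**Working it through.** No arithmetic applies. The threshold has no stated derivation, there is no figure to reproduce, and no rate is given for these events. The check sets the sections side by side.

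1. **Tests in the rule (8.6.2).** An event counts if it is severe hypoglycemia or severe hyperglycemia as defined in 8.1, and if it is thought to be advice-related, glossed as due to excess insulin. The parenthesis has no marker such as *e.g.*, which the protocol uses elsewhere when it means examples (for instance in 8.2 and 8.3).

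2. **Event definition (8.1).** Both routes to a severe hyperglycemic event require DKA or ketosis. Excess insulin is not the mechanism for either.

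3. **Mechanism stated by the protocol (8.5.4 and 8.5.5).** For hypoglycemia, 8.5.4 cites a CGM that over-reads. For hyperglycemia, 8.5.5 cites a CGM that under-reads and so distorts the insulin recommendation. Under that heading, the distortion can only mean too little insulin. Both directions were recognised in 8.5, but only one reached 8.6.2.

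4. **Can the advice be too low?** Yes. Section 1.2 says the system optimizes the patient's "functional insulin therapy parameters (basal doses, insulin sensitivity" factors and carbohydrate ratios. Its bolus calculator subtracts insulin on board and uses a predicted glucose. Section 5.2.1 trains subjects to use it to "calculate insulin doses for meals and corrections". Under 7.1.2.2, CGM+DSS subjects with ketones of at least 0.6 mmol/L take correction insulin as the system recommends, so it advises the dose when ketosis may already be developing.

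5. **Applying the literal rule.**

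| Event | Advice error | Meets the parenthesis | Counts toward more than three |
|---|---|---|---|
| Severe hypoglycemia | Dose too high | Yes | Yes |
| DKA, or ketosis seen at a facility | Dose too low | No | No |

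6. **Does another rule close the gap?**
   - *7.1.2.2:* "Subjects will be required to set the CGM hyperglycemia threshold alarm to a value no greater than 300" mg/dL; ketone testing at 300 mg/dL or above for over 1 hour, or 400 mg/dL or above at any point; staff notified at ketones of 3.0 mmol/L or more. These protect the individual.
   - *5.4:* contacts at 2, 4, 6, 8 and 10 weeks that check for glucose above 300 mg/dL and adverse events. These detect events but set no study-level action.
   - *8.6.1:* one episode ends inControl Advice for that subject, whatever its cause. It cannot respond to a pattern across subjects.
   - *8.2 and 8.3:* Medical Monitor review and reporting to the IRB and FDA. Neither section states a suspension criterion.
   - *8.6.2, second rule:* three serious adverse events from device malfunction stop the study. A poorly functioning CGM may fall under this. Advice that is too low while everything works as designed is not clearly a malfunction. The body of Section 8.4 (Device Issues) is not visible in the copy reviewed, so the reach of this rule cannot be fully judged.

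In the visible text, none of these is clearly a study-level trigger for under-dosing advice without device malfunction.

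**The case against.** The strongest reply is that the rule expressly names severe hyperglycemia, so a sensible reader would not adopt a construction that empties those words. Attaching the parenthesis to hypoglycemia, or treating it as a loose gloss, gives every word effect. That is a fair account of what was probably intended, and it is why this is called a probable drafting error. It does not settle how the text will be applied.

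Second, the causality guideline in 8.2 has no direction: DKA from under-dosing would be recorded as related to the intervention, and the Medical Monitor reviews every form. That makes divergent handling less likely. But relatedness under 8.2 and qualification under 8.6.2 are separate tests, and only the second carries the excess-insulin wording.

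Third, human checks exist. The system advises and does not deliver insulin, the starting basal dose follows the home dose (5.1), and the carbohydrate-counting parameters entered are confirmed with the study physician (5.2.1). These lower the chance of harm but do not repair the rule.

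Fourth, the trigger may rarely be approached. Because 8.6.1 takes a subject off the system after one episode, four events would ordinarily mean four different subjects. With 2:1 randomization that is four of about 88 (132 × 2/3) to 107 (160 × 2/3) users. This argues for modest severity, but a pattern across several subjects is what a study-level rule is meant to catch.

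Finally, saying that excess insulin cannot fit the event is slightly strong, since rebound hyperglycemia after over-treated hypoglycemia is conceivable. The ketosis requirement in 8.1 leaves that exception marginal.

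**Conclusion.** The concern holds. As written, 8.6.2 lists severe hyperglycemia as grounds for suspension and then qualifies it with a cause that fits only hypoglycemia. No visible text extends the qualifier to insufficient insulin. The literal consequence is confined to the suspension rule: DKA from too low a recommendation does not count toward it, though it still ends that subject's use of the system and is still reported. Confidence in the wording conflict is high. The conclusion assumes that the parenthesis limits the term it follows and that the missing text of 8.4 does not define under-dosing advice as a malfunction. Sample size, type I error and the primary analysis are unaffected. It should be corrected because it changes what a stated safety rule counts.

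**What to change.** In 8.6.2, change the parenthesis to read *due to excess or insufficient insulin administration*. Keep the more-than-three threshold and the definitions in 8.1.

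Deleting the parenthesis would also remove the conflict. It would let advice on carbohydrate intake count as well, which is wider than this conflict requires; the sponsor may prefer it if severe hypoglycemia after inadequate snack or exercise advice is meant to count.

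The cost is a one-phrase protocol clarification. Suspension could occur slightly more often, for an event type the rule already names.

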1203 returns a drug, the amount used and unused will be documented, and an explanation for any
1204 inadvertent loss or destruction of supplies will also be recorded.

1205 Ensuring compliance and reconciliation: Site personnel will assess dosing regimen compliance and
1206 drug reconciliation in an ongoing manner. At each subject visit, subject compliance will be evaluated
1207 and documented, including calculating the expected amount of consumed drug given the regimen and
1208 amount of time between visits. This figure will be compared with the amount dispensed minus the
1209 amount the subject returned. Site personnel will question the subject regarding any discrepancies in
1210 these amounts and document the explanation.

1213 Insulin Storage: Insulin will be stored per product labeling as follows:

Insulin	Temperature	Use up to
In use (opened)	Room temperature: up to 86°F	28 days
Not in use (unopened)	Room temperature: up to 86°F	28 days
Not in use (unopened)	Refrigerated: 36°F to 46°F	Expiration date

1214

1215

1216

1217

1218 **10 STATISTICAL CONSIDERATIONS**

1219 The approaches to sample size and statistical analyses are summarized below. A detailed statistical
1220 analysis plan will be written and finalized prior to the completion of the study.

1224 **10.1 Sample Size**

1225 We plan on 132 subjects finishing the study, leading to a potential enrollment of 160, with up to 17.5%
1226 attrition. We base our analysis on our previous decision-support trial [7] which recruited N=120
1227 subjects and concluded with N=96 yielding effect size of 0.2 on key parameters, and on the feasibility
1228 and safety study described in the background. In this study, 11 T1DM pump users tested a prototype of
1229 the DSS leading to an estimated moderate effect size of 0.5 (Cohen D method). Assuming a substantial
1230 reduction of effect size due to (i) the focus on MDI patients, (ii) the presence of CGM in both the
1231 experimental and the control groups, and (iii) the translation of the effect to an uncontrolled
1232 environment similar to the environment of our previous trial [7], we assume a small to medium effect
1233 size. Using the statistical analysis presented below, a 0.15 effect size, with 2 groups randomized in a
1234 ratio of 2:1 (experimental-control), and 3 repeated measures (inter measure correlation of 0.5) leads to
1235 a required sample size of N=132 (expected power of 95.6%) [15].

1236 **10.2 Primary Endpoints Analyses**

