1237 The primary analysis will follow the intention-to-treat principle [16]. It will include all subjects and the
1238 data will be analyzed in the group to which the subjects were assigned through randomization. Percent
1239 in range (70-180 during the day and 80-140 at night) will be computed over each month of data and
1240 entered in a Repeated Measure ANOVA, where the within-between interaction (group x period) will
1241 be studied.

1243 **10.3 Secondary Efficacy Analyses**

1244 In addition to the primary endpoint we will study:

- 1245 • HbA1c: estimated effect size of 0.15; repeated measures ANOVA, 2 groups, 2 measures,
1246 results in power of 90% with current enrollment;
- 1247 • Exposure to hypoglycemia, as measured by the percent of time spent below 70mg/dL and by
1248 the Low BG Index [13]; estimated effect size 0.25; power for repeated measures ANOVA 2x3
1249 >99%;
- 1250 • Exposure to hyperglycemia, as measured by the percent of time spent above 300mg/dL;
1251 estimated effect size 0.2; power for repeated measure ANOVA 2x3 = 99%;
- 1252 • Glucose variability as measured by the Average Daily Risk Range [14] (over 2-week period);
1253 estimated effect size 0.15; power for repeated measure ANOVA 2x6 = 95%.

1255 **10.4 Questionnaires**

1256 The following questionnaires will be completed at the randomization visit:

- 1257 • Diabetes Specific Personality Questionnaire
- 1258 • Clarke Hypoglycemia Awareness Scale [17]
- 1259 • Fear of Hypoglycemia Survey (HFS-II) [18]
- 1260 • Low Blood Sugar Survey
- 1261 • High Blood Sugar Survey
- 1262 • Diabetes Distress Scale
- 1263 • Technology Expectations Survey (CGM+DSS group)

1265
1266 The following questionnaires will be completed at the final visit at week 12:

1267 • Clarke's Hypoglycemia Awareness Scale
1268 • Fear of Hypoglycemia Survey (HFS-II)
1269 • Low Blood Sugar Survey
1270 • High Blood Sugar Survey
1271 • Diabetes Distress Scale
1272 • Technology Acceptance Survey (CGM+DSS group)

1273
1274 For each questionnaire, mean \pm SD values or percentiles appropriate to the distribution will be given
1275 by randomization group for the total score and each subscale. For questionnaires administered to both
1276 randomization groups comparisons will be made using similar ANCOVA models as described above
1277 for the primary endpoints. No formal adjustment will be made for multiple comparisons.

1278
1279 **10.5 Primary Safety Analyses**
1280 All subjects will be included in these analyses.

1281

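### The 95.6% power in section 10.1 requires the group difference in time in range to change by 0.64 to 0.74 SD, which is not a substantial reduction from the pilot d of 0.5

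*Combined protocol and SAP*

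**What the plan says.** Section 10.1 names two sources for the planning effect. One is the earlier decision-support trial, with an effect of 0.2 whose scale is not given. The other is the feasibility study of the prototype: "the DSS leading to an estimated moderate effect size of 0.5 (Cohen D method). Assuming a substantial". Three reasons for a reduction follow, and the section then says: "environment similar to the environment of our previous trial [7], we assume a small to medium effect" size. The value entered is 0.15, with no metric. The remaining inputs are a "ratio of 2:1 (experimental-control), and 3 repeated measures (inter measure correlation of 0.5) leads to" the result, "a required sample size of N=132 (expected power of 95.6" percent. No alpha is stated, and G*Power 3 is the cited software.

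Section 10.2 defines the test: percent time "in range (70-180 during the day and 80-140 at night) will be computed over each month of data and" "entered in a Repeated Measure ANOVA, where the within-between interaction (group x period) will" be studied.

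Section 10.3 gives separate figures for the secondary outcomes. The first is "HbA1c: estimated effect size of 0.15; repeated measures ANOVA, 2 groups, 2 measures", which "results in power of 90% with current enrollment". No correlation is given for any of them.

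Section 1.2 describes the feasibility study as a randomized crossover with two 48-hour periods and puts its effect on time in range above 0.5.

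**The concern.** A reader sees 0.5 reduced to 0.15 and concludes that the trial has 95.6% power for an effect well under a third of the pilot's. That holds only if both numbers are on one scale. Cohen's d is a difference in standard deviations. Cohen's f for an interaction is the spread of the interaction effects over the cells, and the same numeral stands for a much larger difference. If 0.15 is an f, the stated reduction may be partly or wholly a change of units.

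What is at stake is how a null result is read. Taken at face value, section 10.1 puts the chance of missing an effect clearly below 0.5 SD at 4.4%.

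**Working it through.** **Inputs.** From section 10.1: N=132, 2:1 allocation (88 and 44), m=3 measures, correlation ρ=0.5, stated power 95.6%. From section 10.2: the tested term is group by period. Assumed, because the documents do not state them: alpha 0.05, equal variances and compound symmetry.

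**1. Reproduce the stated power.** For Cohen's f, λ = f²·N·m/(1−ρ), with df (m−1) and (N−2)(m−1). With f=0.15:
- Equal groups: λ = 0.0225×132×3/0.5 = 17.82, power 97.2%.
- 2:1 allocation, factor 4×(2/3)×(1/3) = 8/9: λ = 15.84, power 95.3%, against 95.6% stated.

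The same 2:1 formula gives 89.7% for HbA1c (m=2, ρ=0.5 assumed, λ = 10.56), against 90% stated.

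**2. Try 0.15 as d.** Let d_j be the group difference in period j, in SD. Then λ = N·(2/3)(1/3)·Σ(d_j − d̄)²/(1−ρ) = 58.67·Σ(d_j − d̄)². If the difference changes by D between its lowest and highest period, with the middle period anywhere between, the sum of squares lies between D²/2 (linear) and 2D²/3 (step). So λ runs from 29.33·D² to 39.11·D². With D=0.15, λ is 0.66 to 0.88 and power is 10% to 12%. The stated power therefore fits f and does not fit d.

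**3. Convert the stated power to SD.** Power of 95.6% with 2 and 260 df needs λ = 16.12.
- Step: D = √(16.12/39.11) = 0.64.
- Linear: D = √(16.12/29.33) = 0.74.

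These bound every three-period pattern. The conversion uses only N, allocation, ρ, alpha and the stated power, so it does not depend on how 0.15 is read.

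**4. Power at smaller changes.**

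| Change in group difference | Linear | Step |
|---|---|---|
| 0.5 SD | 67.2% (λ=7.33) | 80.1% (λ=9.78) |
| 0.3 SD | 28.4% (λ=2.64) | 36.7% (λ=3.52) |

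Simulation with 88 and 44 subjects (20,000 runs) gave 67.2% and 80.6% at 0.5 SD.

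**5. Sensitivity to alpha.** At 0.10 the needed change is 0.59 to 0.68 SD; at 0.025 it is 0.69 to 0.79 SD.

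**6. HbA1c.** With two measures λ = 14.67·D²/(1−ρ), and 90% power needs λ = 10.67. At N=132 this gives D = 0.60 SD at ρ=0.5, 0.71 at ρ=0.3 and 0.47 at ρ=0.7. Power at a 0.5 SD change is 77%, 62% and 93% respectively.

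**7. Other figures in 10.3.** With 2:1 allocation and ρ=0.5, f=0.2 over three measures gives 99.8% (99% stated). The 2x6 figure is stated as 95%, but f=0.15 gives 99.7% at ρ=0.5 (λ = 31.68) and 94.8% at ρ=0.2 (λ = 19.80).

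**The case against.** **The computation reproduces.** It does, to within a fraction of a point, once 0.15 is taken as f. A reader might infer that the software output or N is wrong; the documents do not support that. The fault lies in what the text says 0.15 represents.

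**The earlier trial's 0.2 is also a stated basis.** This stands in part. If 0.2 is an f, then 0.15 is a reduction from it. Its scale is not given, so this is only a possibility, and it does not make 0.15 a reduction from d=0.5.

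**The needed change might be taken to exceed the pilot effect.** A reader might infer this from 0.64 to 0.74 against 0.5, but it cannot be settled. Section 1.2 says above 0.5, and the crossover's standardiser is not given. If d used the SD of paired differences, 0.5 equals 0.5·√(2(1−ρ)) between-subject SD: 0.67, 0.59, 0.50 or 0.39 at pilot ρ of 0.1, 0.3, 0.5 or 0.7. The first of these lies above 0.64. Even there, 0.64/0.67 = 0.96, a 4% reduction and not a substantial one.

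**The HbA1c power might be thought to fail in the same way.** Section 10.3 does not derive its HbA1c value from the pilot and claims no reduction from 0.5, and the needed change depends on a correlation it does not give. The point there is missing inputs only.

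**A detailed analysis plan is promised.** Alpha and per-endpoint inputs could go there, but the sample-size rationale already stands in 10.1 and a later plan would not correct it.

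**A benefit constant over the three periods produces no interaction.** True, but that concerns the choice of test in 10.2 and should be raised separately.

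**Conclusion.** The point holds for the primary outcome. Section 10.1 attaches 95.6% power to an effect described as substantially reduced from d=0.5, whereas the planned test has that power only for a change of 0.64 to 0.74 SD in the group difference. At 0.5 SD the chance of missing the effect is 20% to 33%, and at 0.3 SD 63% to 72%, not 4.4%. The claimed reduction from the nominal 0.5 and the stated power are not compatible as written.

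This rests on the plan's own N, allocation, number of measures and correlation, and on an assumed alpha of 0.05; at 0.10 the needed change is still above 0.5 SD. It does not establish that the needed change exceeds the pilot effect, or that 132 completers are too few for the effect that will occur. For HbA1c, 90% power corresponds to 0.47 to 0.71 SD for correlations from 0.7 to 0.3, with no inconsistency with the pilot claimed.

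**What to change.** No change to N.

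**Section 10.1.**
- Label 0.15 as Cohen's f for the group-by-period interaction, if that is what was used, and state alpha.
- Give the equivalent change in the group difference, 0.64 to 0.74 SD, and its value in percentage points of time in range. The plan gives no SD for this outcome; the pooled 2-week baseline CGM data could supply one.
- Either delete the statement that the planning effect is a substantial reduction from d=0.5, or restate power for the planned test at or below 0.5 SD (67% to 80% at 0.5 SD; 28% to 37% at 0.3 SD).
- State the scale of the earlier trial's 0.2.

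**Section 10.3.**
- State the metric, correlation and N behind each power figure.
- Give the HbA1c equivalent for the correlation actually used.
- Recheck the 2x6 figure.

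The cost is rewording, a few recomputed numbers, and a less favourable stated power.
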